8.2.1.2. Adverse Event Monitoring with a Systematic Questionnaire

Suicidality will be assessed as required by the US Food and Drug Administration's Division of Neurology for use in clinical trials involving all drugs for neurological indications. Before administering the C-SSRS (Posner et al. 2011), study site personnel will question the patient about any change in the pre-existing condition(s) and the occurrence and nature of any AEs. Nonserious AEs obtained through the questionnaire are recorded and analyzed separately. Only *serious* AEs and AEs leading to discontinuation elicited through the C-SSRS are to be recorded as AEs via eCRF. Serious adverse events must be reported to Lilly or its designee within 24 hours as SAEs. Any suicidal behavior, or suicidal ideation per items 4 or 5 (active suicidal ideation with some intent to act, either without specific plan or with specific plan and intent) would prompt referral of the patient to a mental health professional.

8.2.2. Complaint Handling

Lilly collects product complaints on investigational products and drug delivery systems used in clinical studies in order to ensure the safety of study participants, monitor quality, and to facilitate process and product improvements.

Patients will be instructed to contact the investigator as soon as possible if he or she has a complaint or problem with the investigational product (or drug delivery system such as a prefilled syringe) so that the situation can be assessed.

8.3. Treatment of Overdose

No data are available at this stage of development.

8.4. Safety Assessments

8.4.1. Electrocardiograms

For each patient, a single, 12-lead digital ECG will be collected at the visits shown in the Schedule of Activities (Appendix 2). Electrocardiograms will have a central overread and should be recorded according to the study-specific recommendations included in the ECG manual.

Any clinically significant findings from ECGs that result in a diagnosis should be reported to Lilly or its designee as an AE via eCRF.

8.4.2. Vital Signs

Vital signs will include body temperature, blood pressure, and pulse. Blood pressure and pulse will be measured in triplicate in the sitting position prior to blood draws and study drug administration (see Study Schedule [Appendix 2]).

Any clinically significant findings from vital signs measurement that result in a diagnosis should be reported to Lilly or its designee as an AE via eCRF.

8.4.3. Laboratory Tests

For each patient, laboratory tests detailed in Appendix 3 should be conducted according to the Schedule of Activities (Appendix 2).

Any clinically significant findings from laboratory tests that result in a diagnosis should be reported to Lilly or its designee as an AE via eCRF.

In addition, an immunogenicity plasma sample will be collected, when possible, for any patient who experiences a potential systemic allergic/hypersensitivity reaction during the study as judged by the investigator. This immunogenicity plasma sample should be collected immediately or as soon as possible, taking into consideration the availability and wellbeing of the patient. Exact date and time of the sample should be recorded on the laboratory requisition form.

8.4.4. Other Tests

Not applicable.

8.4.5. Safety Monitoring

Investigators are responsible for monitoring individual patient safety throughout the trial. If a study patient/subject experiences elevated ALT \geq 3X ULN, ALP \geq 2X ULN, or elevated TBL \geq 2X ULN, clinical and laboratory monitoring should be initiated by the investigator. Details for hepatic monitoring depend upon the severity and persistence of observed laboratory test abnormalities. To ensure patient/subject safety and comply with regulatory guidance, the investigator is to consult with the Lilly CRP/CRS regarding collection of specific recommended clinical information and follow-up laboratory tests. See Appendix 4.

Neurological examinations will be conducted at screening, Month 3, Month 6, Month 9, and Month 12 of treatment, as well as at the final visit of the follow-up period or early termination visit in order to assess for any signs of pre-existing or treatment-emergent neurological abnormalities such as stroke or other cerebrovascular events. If a study patient experiences signs of a cerebrovascular event, appropriate follow-up and clinical management should be conducted by the investigator, and the Lilly CRP/CRS should be consulted regarding collection of further clinical information and follow-up testing.

Lilly will periodically review evolving aggregate safety data within the study by appropriate blinded methods. In addition, safety data for the trial will also be reviewed periodically by an independent Data Monitoring Committee (DMC; an advisory group for this study formed to protect the integrity of data; refer to Interim Analyses section). In the event that safety monitoring uncovers an issue that needs to be addressed by unblinding at the group level, members of the DMC can request additional analyses of the safety data.

8.5. Pharmacokinetics

At the visits and times specified in the Schedule of Activities (Appendix 2), venous blood samples of approximately 2.5 mL each will be collected to determine the serum concentrations

of LY2951742. A maximum of 3 samples may be collected at additional time points during the study if warranted and agreed upon between both the investigator and sponsor. Instructions for the collection and handling of blood samples will be provided by the sponsor.

When a blood sample is collected, the time and date of last dose administration prior to blood sampling should be recorded. The actual date and time (24-hour clock time) of each sampling will be recorded. LY2951742 concentration information that may/would unblind the study will not be reported to investigative sites or blinded personnel until the study has been unblinded. Bioanalytical samples collected to measure investigational product concentration will be retained for a maximum of 1 year following last patient visit for the study.

A validated assay will be used to determine serum LY2951742 concentrations. Samples will be analyzed at a laboratory approved by the sponsor.

It is intended that blood samples collected from patients who received placebo should not be analyzed for determination of serum concentrations of LY 2951742.

8.6. Pharmacodynamics

[figure not shown]
At the visits and times specified in the Schedule of Activities (Appendix 2), venous blood samples will be collected to determine the plasma concentrations of CGRP. A maximum of 3 samples may be collected at additional time points during the study if warranted and agreed upon between both the investigator and sponsor. Instructions for the collection and handling of blood samples will be provided by the sponsor. When a blood sample is collected, the time and date of last dose administration prior to blood sampling should be recorded. The actual date and time (24-hour clock time) of each sampling will be recorded.

A validated drug-tolerant assay will be used to determine plasma CGRP concentrations. Samples will be analyzed at a laboratory approved by the sponsor.

Plasma CGRP concentration information that may/would unblind the study will not be reported to investigative sites or blinded personnel until the study has been unblinded.

Bioanalytical samples collected to measure CGRP will be identified by the patient number (coded) and retained for a maximum of 1 year following last patient visit for the study at a facility selected by the sponsor.

8.8. Biomarkers

Blood samples for non-genetic biomarker research will be collected at the times specified in the Schedule of Activities (Appendix 2), where local regulations and ERBs allow.

Samples will be used for research on the drug target, disease process, pathways associated with migraine headache and/or other pain conditions, mechanism of action of LY2951742, and/or research method or in validating diagnostic tools or assay(s) related to migraine headache and/or other pain conditions.

All biomarker samples will be coded with the patient number. These samples and any data generated can be linked back to the patient only by the investigator site personnel. Samples will be destroyed according to a process consistent with local regulations.

Samples will be retained for a maximum 15 years after the last patient visit for the study, or for a shorter period if local regulations and ERBs impose shorter time limits, at a facility selected by the sponsor. This retention period enables use of new technologies, response to regulatory questions, and investigation of variable response that may not be observed until later in drug development or when the drug is commercially available.

8.8.1. Samples for Immunogenicity Research

Where local regulations and ERBs allow, blood samples for immunogenicity testing will be collected to determine antibody production against LY2951742 as specified in the Schedule of Activities (Appendix 2). Immunogenicity will be assessed by a validated assay designed to detect anti-drug antibodies in the presence of the investigational product. Antibodies may be further characterized and/or evaluated for their ability to neutralize the activity of LY2951742.

Samples will be retained for a maximum of 15 years after the last patient visit for the study, or for a shorter period if regulations and ERBs impose shorter time limits, at a facility selected by the sponsor. The duration allows the sponsor to respond to future regulatory requests related to LY2951742.

8.9. Health Economics

Health economic, disability and quality of life assessments of LY2951742 in patients with migraine will be based on the following scales:

Migraine Disability Assessment Scale (MIDAS): The MIDAS was designed to quantify headache-related disability over a 3-month period. This instrument consists of five items that reflect the number of days reported as missing, or with reduced productivity at work or home and social events; higher values are indicative of more disability (Stewart 1999; Stewart 2001). This instrument is considered highly reliable and valid; and is correlated with clinical judgment regarding the need for medical care (Stewart 1999; Stewart 2001).

Migraine-Specific Quality of Life questionnaire (MSQ v2.1): The MSQ v2.1 is a self-administered health status instrument, and was developed to address physical and emotional limitations of specific concern to individuals suffering from migraine headaches. The instrument consists of 14 items that address 3 domains: (1) Role Function-Restrictive; (2) Role Function-Preventive; and, (3) Emotional Function (Jhingran 1998). The instrument was designed with a 4-week recall period, and is considered reliable, valid and sensitive to change in migraine (Jhingran 1998; Rendas-Baum 2013). Clinically meaningful differences for each domain have been established and are widely used in the literature.

Health Care Resource Utilization (HCRU) and Employment Status: The HCRU will be solicited by study personnel while documenting patient responses. The HCRU consists of 3 questions, asking about hospital emergency room visits, overnight stays in a hospital, and any other visits with a healthcare professional that occurred since their last study visit. Patients are also specifically asked about the number of health care events that are related to migraine headaches, outside of visits associated with their participation in the clinical trial. The baseline visit will include the same questions, however with the frame of reference being over the last 6 months. A question on employment status is also solicited, given the correlation and potential confounding with health outcomes measures.

9. Statistical Considerations and Data Analysis

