Appendix 2. Schedule of Activities

Schedule of Activities, Protocol I5Q-MC-CGAI (Double-Blind Treatment Phase)

Study Period (SP)	SP I Screening	SP II Prospective Baseline	SP III Double-Blind Treatment							
(Target) Interval (days) since previous visit			30-45	14	16	30	30			
Allowable range (days) between visits	3-45	30-40 ^a								
Interval allowance (days)				+/- 1	+/- 3	+/- 2	+/- 2			
Visit	1	2	3	4 ^b	5	6	7			
Month			0	0.5	1	2	3			
Assessments and Procedures										
Informed consent	X									
Inclusion/exclusion	X	X	X							
Demographics	X									
Physical examination	X									
Neurological examination ^c	X						X			
Height	X									
Weight	X						X			
Waist/hip circumference	X									
Medical history	X									
Pre-specified migraine history		X								
Substance use	X									
ECG ^d	X		X				X			
Vital signs ^e	X		X		X	X	X			
Adverse events	X	X	X	X	X	X	X			
Concomitant medications	X	X	X		X	X	X			
ePRO training		X								
ePRO daily patient entries		X	X	X	X	X	X			
Patient training video			X							

Clinical Laboratory Tests an	nd Sampling (Sahadula					
Hematology	X	Schedule 	X				X
Clinical chemistry	X		X^{f}				X ^f
HDL	X		X ^e				Xe
HbA1c	Λ		X				X
Fasting insulin/							
fasting C-peptide			X^{e}				X ^e
Urinalysis ^g	X		X				X
Serum Pregnancy (for women of childbearing potential) or FSH at V1 (all other female patients) ^h	X						X
Urine pregnancy ^h			X		X	X	
Urine drug screen	X						
Immunogenicity ⁱ			X	X	X	X	X
Biomarker storage sample ⁱ	X	X	X		X		
CCI							
PK blood sample ⁱ				X	X	X	X
CCI							
RNA			X				X
Study drug administered ^j			X		X	X	X (if continuing to OLE)
Scales, Questionnaires, and	Outcome Mea	asures					
MIDAS			X				X
MSQv2.1			X		X	X	X
HCRU/Employment			X		Х	X	X
Status					23	7.	71
Non-migraine chronic pain assessment ^k			X				X
PGI-S			X		X	X	X
1 01 5							
PGI-I					X	X	X

Schedule of Activities, Protocol I5Q-MC-CGAI (Open-Label and Post-Treatment Phases)												
Study Period (SP)			SP V Post-treatment									
(Target) Interval (days) since previous visit	30	30	30	30	30	30	30	30	30	60	60	
Interval allowance (days)	+/- 2	+/- 2	+/- 2	+/- 2	+/- 2	+/- 2	+/- 2	+/- 2	+/- 2	+/- 5	+/- 5	ET
Visit	8	9	10	11	12	13	14	15	16	17	18	
Month	4	5	6	7	8	9	10	11	12	14	16	
Assessments and Pro	ocedures											
Weight			X			X			X		X	X
Neurological examination ^c			X			X			X		X	X
ECG ^d			X						X		X	X
Vital signs ^e	X	X	X	X	X	X	X	X	X	X	X	X
Adverse events	X	X	X	X	X	X	X	X	X	X	X	X

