^a The eligibility period of the prospective baseline assessment will last from 30 to 40 days. Investigators and patients may have up to an additional 5 days to schedule their Visit 3 appointment (beyond the 40 days); however, eligibility will be based on the 30- to 40-day period.

^b Visit is to include a review of any spontaneously reported adverse events and collection of blood samples for immunogenicity, PK, and CGRP plasma.

^c A neurological exam will be conducted at screening, Month 3 (final visit of double-blind treatment), Months 6, 9, and 12 (open-label treatment), and Month 16/early termination in order to assess for any signs of pre-existing or treatment-emergent neurological abnormalities such as stroke or other cerebrovascular events.

^d Electrocardiograms (ECGs) will be performed at Visit 1, Visit 3, Visit 7, Visit 10, Visit 16, and Visit 18 or early termination. Note: The Visit 3 ECG should be collected prior to blood draws and dosing. Patients must be supine for approximately 5 to 10 minutes before ECG collection and remain supine but awake during ECG collection.

^e Vital signs taken at every office visit will include body temperature, blood pressure and pulse. Blood pressure and pulse will be measured in triplicate in the sitting position and should be measured prior to blood draws. Blood pressure will be assessed by utilizing a calibrated machine.

^f Chemistry labs collected at Visit 3, Visit 7, Visit 10, Visit 13, Visit 16, and Visit 18 or early termination must be fasting. Fasting is defined as no food or drink, except water, for at least 8 hours prior to testing.

g In the event of a positive urine leukocyte esterase result, a repeat urine sample will be collected and shipped to the central laboratory.

^h A positive urine test must be followed by a serum pregnancy test for confirmation.

Immunogenicity and storage sample, and PK blood sampling to be performed at the indicated visits and prior to dose administration if the visit is a dosing visit. Samples will be taken in the event of early termination. Immunogenicity samples also may be collected in the event of a systemic allergic/hypersensitivity reaction (see Section 8.4.3). The exact date and time of the samples should be recorded.

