5.4.3.3. Health Care Resource Utilization (HCRU) and Employment Status

Health Care Resource Utilization (HCRU) will be solicited by study personnel while documenting patient responses. Data to be collected include whether patients have hospital emergency room (ER) visits, overnight hospital stays, and other visits with healthcare professional, and, if yes, the numbers of above visits, as well as the numbers of above visits that are related to migraine headaches. Visits associated with their participation in the clinical trial should not be included in the responses. A question on employment status is also solicited, given the correlation and potential confounding with health outcomes measures.

At the baseline visit, these questions will be asked for the time frame of past 6 months. At postbaseline visits, the questions will be asked for the time from last visit to current visit.

Health Care Resource Utilization data will be analyzed at every 3-month interval. Baseline 3 months value will be derived as the baseline number divided by 2. Data from monthly Visit 5 to Visit 16 will be added for every 3 months. If missing data occur in more than 2 monthly visits, the 3-month period will have a missing data point.

If there is at least 1 non-missing data for HCRU for the patient, then all the other missing HCRU data for the same patients will be imputed as 0.

Data from the 3-month double-blind period will be analyzed relative to 3-month baseline data. Data from the entire 12-month treatment period (double-blind plus open-label periods) will also be analyzed in 3-month increments relative to the 3-month baseline data.

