5.5.11. Quality-of-Life (QoL) Analyses

The mean change from baseline to each postbaseline visit for SP III and SP III/IV/V for MSQ (including Role Function-Restrictive, Role Function-Preventive, Emotional Function, and total score), as defined in Section 5.4.3 will be evaluated using MMRM as described in Section 5.5.10.1.

Mean change from baseline to LOCF endpoint in the 3-month treatment phase for above quality of life measures will be evaluated using the ANCOVA model as described in Section 5.5.1.1.

The change from baseline to Month 3 score in MIDAS (item scores and total score) will be evaluated using the ANCOVA model as described in Section 5.5.1.1. The mean change from baseline to each postbaseline visit for SP III/IV and for SP III/IV/V for MIDAS (item scores and total score) will be evaluated using MMRM as described in Section 5.5.10.1.

Indicators of the MSQ Role Function Restrictive domain responders and MIDAS responders will be analyzed using GLIMMIX (as described in Section 5.5.10.3). Threshold for MSQ Role Function Restrictive domain response will be derived as outlined in "Statistical Analysis Plan for Psychometric Properties of the MSQv2.1 Role Function-Restrictive Domain". The threshold for MIDAS response will be a 50% improvement from baseline in MIDAS total score.

For the HCRU, the following measures will be analyzed:

- number of hospital emergency room (ER) visits
- number of overnight hospital stays
- number of other visits with healthcare professional
- number of hospital ER visits related to migraine headache
- number of overnight hospital stays related to migraine headache
- number of other visits with healthcare professional related to migraine headache

All of the above measures for the HCRU will be analyzed with a repeated measures negative binomial regression analysis fitted with SAS PROC GLIMMIX. The model includes pooled country, month, baseline medication overuse (yes versus no), concurrent prophylaxis use (yes versus no) and treatment-by-month interaction, as well as the continuous fixed covariates of

baseline and baseline-by-month interaction, log (number of actual number of days within every 3 month/90) as the offset in the model. In case of non-convergence, pooled country and/or baseline-by-month interaction may not be included in the model.

Employment status at each visit will be summarized separately for each treatment groups.

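### As worded, the health care utilization (HCRU) recall at Visit 5 reaches back only to Visit 4, so about 14 of the 90 double-blind days are not covered

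*Protocol*

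**What the plan says.** **Recall window.** Protocol 8.9 describes three HCRU questions, asked by study personnel. They cover emergency room visits, overnight hospital stays and "any other visits with a healthcare professional that occurred since their last study visit". SAP 5.4.3.3 has the same anchor: "At postbaseline visits, the questions will be asked for the time from last visit to current visit". For baseline it says: "At the baseline visit, these questions will be asked for the time frame of past 6 months".

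**When it is asked.** In the Schedule of Activities (Protocol Appendix 2) the HCRU row is marked at Visits 3, 5, 6 and 7, and at every visit from 8 to 18. The Visit 4 cell is blank. Visit 4 is a scheduled visit (Month 0.5), and its footnote describes a limited one: "Visit is to include a review of any spontaneously reported adverse events and collection of blood samples for immunogenicity, PK, and CGRP plasma".

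**How it is analyzed.** SAP 5.4.3.3 builds quarterly totals: "Data from monthly Visit 5 to Visit 16 will be added for every 3 months". For the comparator it says: "Baseline 3 months value will be derived as the baseline number divided by 2". The double-blind total is set against that baseline, and the 12-month treatment period is analyzed in quarters against it too. SAP 5.5.11 fits a repeated measures negative binomial model with baseline as a covariate and "log (number of actual number of days within every 3 month/90) as the offset in the model".

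**The concern.** Visit 4 is the only scheduled post-baseline visit without HCRU, so it is the only place where a recall tied to the previous visit breaks. A site that follows the wording asks at Visit 5 about the time since Visit 4. The baseline question looks backward from Visit 3 and cannot fill the gap. Nothing else in the schedule asks the HCRU questions about the two weeks after the first dose.

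The analysis then treats the total of Visits 5 to 7 as a full quarter. Two planned readings would be distorted: the change from baseline in the double-blind period, which is a listed secondary endpoint, and the comparison of the first quarter with the open-label quarters, which have no mid-month visit and so no gap.

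**Working it through.** **Inputs**
- Target visit intervals from Appendix 2: "30-45 14 16 30 30". The first entry is Visit 2 to Visit 3. The others are Visit 3 to 4 (14 days), 4 to 5 (16), 5 to 6 (30) and 6 to 7 (30).
- Allowances from the same table: +/-1, +/-3, +/-2 and +/-2 days.
- HCRU visits after baseline in the double-blind period: 5, 6 and 7.
- Offset denominator from SAP 5.5.11: 90 days.

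**Step 1. Reproduce the plan's period.** 14 + 16 + 30 + 30 = 90 days, which agrees with the 90 in the offset.

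**Step 2. Days covered under the literal wording.** Add the intervals that end at a visit where HCRU is asked: 16 + 30 + 30 = 76. Days not covered: 90 - 76 = 14. Share missed: 14/90 = 15.6%.

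**Step 3. Range over the visit windows.**
- Smallest share: Visit 4 early, the other intervals long. 13/(13 + 19 + 32 + 32) = 13/96 = 13.5%.
- Largest share: Visit 4 late, the other intervals short. 15/(15 + 13 + 28 + 28) = 15/84 = 17.9%.

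**Step 4. Effect on the level within an arm.** Assume a constant event rate, no true change, literal application at every site, and an offset that counts every day of the quarter.
- Double-blind quarter against baseline: 76/90 = 0.844, a fall of 15.6% (log scale: ln 0.844 = -0.169).
- First open-label quarter against double-blind quarter: 90/76 = 1.18, a rise of about 18%.

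**Step 5. Effect on the contrast between arms.** The factor 76/90 applies to all three arms. If the rate ratio is constant over the quarter, the factor cancels: (0.844 x drug rate)/(0.844 x placebo rate) = drug rate/placebo rate. The cost is precision. With Poisson counts, the standard error of the log rate ratio grows by the square root of 90/76 = 1.09, about 9%.

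**Step 6. After the correction.** If the Visit 5 recall starts at Visit 3, coverage is 30 + 30 + 30 = 90 of 90 days.

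**The case against.** **The form is not available.** The HCRU form is not among the documents; the protocol and SAP only describe it. SAP 5.4.3.3 calls the reports monthly, which fits a Visit 5 report meant to cover all of Month 1. Visit 4 is a limited visit, with neither vital signs nor concomitant medications marked, and staff might take the last visit to mean the last full monthly one. This stands. A reader might infer that the first two weeks were never counted, but the documents do not support that. They show only that the written rule leaves those days out. If practice differs from the text, the text still needs correcting. If sites differ among themselves, Month 1 coverage is 16 days at some and 30 at others, and no single offset is right.

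**The treatment comparison.** A reader might also infer a biased drug-placebo result. The documents do not support that either: the schedule is the same in all arms, and the planned model uses baseline as a covariate with an offset, so a common factor goes into the level and not the contrast. What remains is the loss of precision, and any arm difference confined to the first two weeks, which would be missed.

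**The offset.** Its definition in SAP 5.5.11 is loosely worded and does not say which days count. All days in the interval is the natural reading, but days covered by the reports are not excluded.

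**Other imperfections.** SAP 5.4.3.3 sets missing HCRU data to zero once a patient has one non-missing value, so the quarterly totals are not clean 90-day counts anyway. This makes the 16% and 18% conditional illustrations. It does not remove the gap.

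**Conclusion.** The point holds for the rule as written and is minor. About 14 of the 90 double-blind days (15.6%; 13.5% to 17.9%) fall outside every HCRU recall window, and the SAP states no compensation for this. The spurious fall of about 16% and the later rise of about 18% rest on the Step 4 assumptions, above all literal application at all sites, which the documents cannot confirm. They concern levels within an arm and the quarterly series. HCRU is among the other secondary endpoints, outside the multiplicity-controlled testing, so no primary or key secondary conclusion depends on it.

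**What to change.** - **Recall.** In protocol 8.9, SAP 5.4.3.3 and the HCRU form, start the recall at the last visit at which these questions were asked, and state that for Visit 5 this is Visit 3.
- **Offset.** In SAP 5.5.11, define the offset as the number of days covered by the recall in each quarter, divided by 90.
- **Data already collected.** First confirm from the form and the site instructions which period was asked about at Visit 5. Use the days from Visit 4 to Visit 7 as the offset only for records where the recall began at Visit 4. Applied to records that already reached back to Visit 3, that shorter offset would inflate the rate by about 18% (90/76).

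The cost is a wording change in three places and a clearer offset definition, plus a check of the form and instructions for existing records. No visit or procedure is added. Recall at Visit 5 lengthens from about 16 to about 30 days, the same as at Visits 6 and 7. If the form already reaches back to Visit 3, correcting the protocol and SAP wording is enough.
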